Calibration Phase I. The calibration phase of this study is designed to gather data to assist in developing an equation to account for the lag in TAC readings and transform these readings into an approximation of alcohol breath readings. In this calibration phase subjects will be given a measured dose of alcohol to achieve a peak BAL level of 0.05 g/dL after a one hour drinking session. The volume of alcohol will be calculated using an online tool developed by UW-Madison (<http://dionysus.psych.wisc.edu/WebCMS/baccalc.htm>) based on a formula described by Watson [14]. The hour-long drinking session will be followed by a five hour observation period to ensure that subject reach peak TAC. Blood alcohol level will be measured simultaneously using the transdermal sensors and the breathalyzer for the duration of the drinking period and observation period. Breathalyzer readings will be taken every 15 minutes during the entire experiment and transdermal sensors will log data continuously. To ensure residual alcohol in subjects' mouths does not provide a false breath alcohol reading, subjects will rinse their mouth twice with water after consuming a saltine cracker prior to each breathalyzer given while the subject is consuming alcohol. Subjects will remain in the drinking lab for up to five hours to allow for measurement of the peak transdermal alcohol concentration. Given the length of observation, we estimate that subjects will fully metabolize the alcohol they received during the calibration session and they will have a BAL of 0.00 g/dL when the calibration session is over. In the event that a drinking session is halted or the subject has a very slow rate of metabolism, we require that subjects remain in the laboratory until their BAL, as measured by breathalyzer, reaches 0.04 g/dL or less. The drinking session will be video-recorded to provide a record of the exact timing of breathalyzer readings. If methodology or safety issues are uncovered during the Phase I of this study, the protocol may be amended to address these issues prior to completing Phase II.

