Validation Phase II. Data from Phase I of this study will be used to develop a model to account for the lag in transdermal sensor readings relative to breathalyzer readings. Once all subjects have completed Phase I and the calibration model is complete, subjects will return to the laboratory to complete Phase II of the study. Given the expected time lag between Phase I and Phase II, eligibility will be re-assessed prior to the Phase II drinking session to ensure subject safety (see appendix A for schedule of events). If the subject remains eligible for Phase II of the study, the Phase II validation drinking session will be scheduled within 14 days of re-assessing eligibility. During the validation drinking session subjects will be given a measured dose of alcohol to achieve a peak BAL level of 0.05 g/dL after a one hour drinking session. The drinking period will be followed by a three-hour observation period. Blood alcohol level will be measured simultaneously using the transdermal sensors and the breathalyzer for the duration of the drinking period and observation period. Breathalyzer readings will be taken every 15 minutes during the entire experiment and transdermal sensors will log data continuously. To ensure residual alcohol in subjects' mouths does not provide a false breath alcohol reading, subjects will rinse their mouth twice with water after consuming a saltine cracker prior to each

Calibration Study of a Wearable Noninvasive Blood Alcohol Monitor

Final V1.8 4.24.19

breathalyzer given during the drinking period. Subjects will remain in the laboratory until their BAL, as measured by breathalyzer, reaches 0.04 g/dL or less.

Subjects: Subjects will be recruited through radio advertisements, newspaper advertisements, study flyers, social media, and internet postings. Interested subjects will be screened by telephone to determine initial eligibility prior to the baseline assessment.

6 Potential Risks and Benefits

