have access to any personal electronic devices for this phase. Subjects will consume crackers and water just prior to the first breathalyzer reading during this phase. This observation period will be video recorded to confirm exact times of BAL readings taken with the breathalyzer. Subjects will be monitored during the observation until their blood alcohol level is ≤ 0.0 g/dL and they are not behaviorally impaired to leave. Four hours after consuming alcohol subject will be given a light meal that is approximately 375 calories. Study staff will assess intoxication, sedation, and adverse effects during this observation period. Subjects will also have access to snacks (e.g. chips, granola bars) and non-alcoholic beverages if the time needed to reach ≤ 0.04 g/dL exceeds the 5-hour observation period. Subjects will be required to have a plan for transportation home that does not involve driving or riding non-motorized transportation (e.g., bike, scooter).

Phase II eligibility determination session

Once all subjects have completed phase I of the study and the model for adjusting TAC readings has been developed, subjects will be invited back to the lab to complete phase II of the study. Eligibility will be re-assessed to ensure subject safety prior to completing the second drinking lab (see appendix A for schedule of testing events).

Phase II BAL validation session

Within 14 days of subjects completing the Phase II eligibility Determination session, subjects will return to the clinic to complete the Phase II BAL validation session. This second alcohol lab visit is divided into the same four phases as the Phase I BAL calibration session: 1) Screening, 2) Zero BAL observation, 3) Alcohol Administration, and 4) Observation. The procedures for this second alcohol lab session are the same with a few exceptions:

- 1) Subjects will be wearing second generation wristwatch sensors.
- 2) TAC readings will be converted into estimated breathalyzer BAL readings based on the model developed in Phase I.
- 3) The observation period will last only 3 hours (or longer if needed for BAL to reach ≤ 0.04 g/dL).

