Predicted BAL that will be determined from TAC data are expected to be equivalent to BrAc concentrations. We, therefore hypothesize that there will be a strong correlation between BAL and BrAc measurements obtained at the same time points for the individual subjects. The reference breathalyzer response is known to be linear over the range of expected blood alcohol levels in the study [23]. Therefore, the breathalyzer and predicted BAL values are expected to be linearly related to each other. To confirm the hypothesis that these values are highly linearly related an analysis will be conducted in which repeated measures correlation coefficient (rcmm) between BrAc and BAL will be obtained. In contrast to a simple correlation analysis of data in which repeated measures collected from individual subjects are used, here will be no violation of the assumption of independence of observations when rcmm values are utilized as the measure of the extent of correlation between these values [Bakdash and Marrusich, 2017].

Calibration Study of a Wearable Noninvasive Blood Alcohol Monitor
Final V1.8 4.24.19

Data obtained in the validation phase of this study will be analyzed using the proc glm procedure for SAS 9.4. This data will include values for individual subjects obtained for each time-point at which BrAc measurement were made and corresponding predicted BAL values determined for these subjects. This data will be analyzed using following general linear model:

BAL= BrAc sub

This model is equivalent to an analysis of covariance model in which subjects (sub) are a covariate. This model will allow for the determination of whether BrAc and BAL values are significantly related to one another. The correlation coefficient [rcmm] for relationship between BAL and BrAc will be determined using the following equation first mentioned by Bland and Altman [24] with sum of squares values being obtained from the results of our glm analysis: $rcmm = \text{square root} [\text{Sum of Squares BAL} / (\text{Sum of Squares BAL} + \text{Sum of Squares Residual})]$

Since both BrAc and BAL measurements are hypothesized to be linear, the rcmm value is expected to be >0.80 with high correlation power. The statistical null hypothesis is that the predicted BAL measurements are not related to the standard breathalyzer measurements. The study is designed to maintain a probability of Type I and Type II error rates with respect to the null hypothesis at $p<0.05$.

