12.2 Sample Size Determination

Calibration Study of a Wearable Noninvasive Blood Alcohol Monitor

Final V1.8 4.24.19

Power analysis: Eight concurrent readings of breathe (BAL) and transdermal alcohol concentration (TAC) will be obtained from the wristwatch sensor and the breathalyzer starting 15 minutes after the start of subject alcohol consumption to the end of the 60 minute drinking session. An additional 20 concurrent readings will be collected during the 5 hour observation period in phase I, and an additional 12 concurrent readings in the 3-hour observation period in phase II. This means that a possible 28 (Phase I) or 20 (phase II) points may be available for this analysis if only pairs of data are used for which values for both devices exceed zero. However, the sensitivity of the wristwatch sensor in human subjects is currently unknown, and so fewer than 20 data points may be of use for our analysis.

Data will be analyzed using a repeated measures correlation (rcmm) procedure described by Bland and Altman [24] and Bakdash and Marisich [25]. For the wristwatch device to be considered to be useful the r value for the correction between BrAc and predicted BAL measures must exceed 0.9. Cohen [26] defines a large effect size as being $r=0.5$. Bakdash and Marish provide power curves for the rcmm procedure. These curves indicate that for a large effect size ($r=0.5$) that the power approach 99% when data from only 10 points are available for sample size of about 7. We anticipate a repeated measures correlation value of at least 0.8 and hope to observe a correlation of 0.9. Bakdash and Marisich [25] indicate the degrees of freedom for determining rcm values can be determined using the following equation:

$$Df = (\text{Number of subjects}-2) \times (\text{number of data points} - 1).$$

The degrees of freedom can be used to determine the corresponding sample size, with the degrees of freedom for standard tables of power analysis being equal to $N-2$ ($Df=N-2$). Using this relationship we use the Proc Power procedure for Pearson correlations in SAS to determine the power for 21 data points collected for 9 subjects and 10 datapoints for 5 subjects. In both of these analyses the calculated power value was > 0.995 for rcm of 0.8 or 0.9.

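### Both sessions impose the same drinking schedule, so r > 0.9 cannot by itself show that the watch carries information beyond the shared time course; a time-only benchmark should be reported beside it

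*Combined protocol and SAP*

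**What the plan says.** **Schedule.** Section 5 (Study Design) describes Phase I as a session in which "subjects will be given a measured dose of alcohol to achieve a peak BAL level of 0.05 g/dL after a one hour drinking session". For Phase II it says: "During the validation drinking session subjects will be given a measured dose of alcohol to achieve a peak BAL level of 0.05 g/dL", again after one hour of drinking. Breath readings are taken every 15 minutes in both. Section 9, on the Phase II validation session, says "The procedures for this second alcohol lab session are the same with a few exceptions". The listed exceptions are a second-generation watch, conversion of transdermal readings through the Phase I model, and a shorter follow-up: "The observation period will last only 3 hours", against five in Phase I. The Phase I breath curve therefore covers every Phase II time point.

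**Criterion.** The primary outcome (Section 4.2.1) is the repeated measures correlation in the second session. Section 12.1 states: "The statistical null hypothesis is that the predicted BAL measurements are not related to the standard breathalyzer measurements". Section 12.2 adds the threshold: "For the wristwatch device to be considered to be useful the r value for the correction between BrAc and predicted BAL measures must exceed 0.9". It is a point value, with no confidence limit and no reference predictor.

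**Other checks.** Section 12.1 plans Pearson correlations of Cmax and of Tmax (expected to be at least 0.8, p < 0.05) and inspection of each subject's curves. Section 9 includes a one-hour zero-BAL period to look for false positive readings. None of these enters the usefulness rule.

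**The concern.** Repeated measures correlation removes each subject's mean and scores only the rise and fall within the subject. Here the protocol itself imposes most of that rise and fall: everyone drinks over the same hour towards the same peak and is then followed while alcohol clears. Anything with roughly that shape against the clock will correlate strongly with breath alcohol.

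A high r therefore shows that predicted BAL tracked breath alcohol under this one schedule. It does not show how much of the agreement is information about the individual's alcohol level and how much is the shared time course. The difference matters because the intended uses (consumer monitoring, outcome measurement in trials) are settings where no protocol fixes when drinking starts or how it proceeds.

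**Working it through.** **1. The plan's own figures.** Section 12.2 takes Df = (subjects − 2) × (points − 1) and N = Df + 2.
- 9 subjects × 21 points: Df = 7 × 20 = 140, N = 142. Power against zero correlation (Fisher z, two-sided 0.05) is above 0.9999 at r = 0.8 and 0.9.
- 5 subjects × 10 points: Df = 3 × 9 = 27, N = 29. Power is 0.9999 at r = 0.8 and above 0.9999 at 0.9.
- Fallback Pearson correlation, n = 9, r = 0.8: power 0.820 by the t test.

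These agree with the stated values (> 0.995 and 0.82). All of them are power against zero correlation.

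**2. How much the test against zero demands.** The smallest significant r is t / √(t² + Df). With Df = 140 and t = 1.977 this is 1.977 / √(3.91 + 140) = 0.165. The 0.9 threshold is therefore the only real hurdle in the primary analysis.

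**3. A predictor with no watch data.** The predictor is the mean breath curve of 12 Phase I subjects, by time since drinking began, used unchanged for each of 9 Phase II subjects.
- From the documents: one-hour drinking, target 0.05 g/dL, readings every 15 minutes (4 in the drinking hour + 12 in observation = 16), and pairs with both values above zero.
- Assumed, because the documents give none of it: first-order absorption 5/h (CV 40% between and 25% within subject), zero-order elimination 0.015 g/dL/h (15% and 10%), dose/volume error (10% and 8%) and breath noise SD 0.002 g/dL. These spreads were scaled up and down together to vary the CV of the peak.
- Statistic: the within-subject correlation, which is what the Section 12.1 model estimates. There were 1,000 trials per setting.

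| CV of peak breath alcohol | Median r | Trials with r > 0.9 |
|---|---|---|
| 10% | 0.984 | 100% |
| 15% | 0.967 | 100% |
| 20% | 0.942 | 96% |
| 26% | 0.913 | 69% |
| 31% | 0.883 | 30% |
| 42% | 0.811 | 2% |

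**4. Sensitivity.**
- Adding four zero-BAL points per subject at a CV of 20% raises the median to 0.951, with 99% above 0.9.
- Section 12.2 counts eight readings in the drinking hour, hence 20 in Phase II. A run with 20 points and a slightly lower dose gave 0.934 and 92%.
- A second set of kinetic assumptions gave 98% above 0.9 at a CV of 18%, 55% at 26% and 13% at 37%.
- A third, more favourable set gave 100% at about 15%, 76% at about 30% and 17% at about 43%.

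The pattern is stable, but the exact crossing point is not.

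**5. Would a confidence limit help?** For the lower 95% limit to exceed 0.9 at N = 142, the observed z must exceed arctanh(0.9) + 1.96/√139 = 1.472 + 0.166 = 1.638, that is, r of about 0.927. The time-only curve also exceeds that when spread is low, so a stricter version of the same threshold does not settle the question.

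**6. What does separate the two cases.** Add the time-only curve to the model and take the partial within-subject correlation of predicted BAL with breath alcohol. At a peak CV of 18% it was about 0 for a signal carrying only the shared shape, and about 0.5 to 0.65 for a simulated genuine sensor.

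**The case against.** **The time-only curve is not what the trial tests.** Predicted BAL is derived from transdermal readings, and nothing in the documents makes elapsed time an input to the model. A dead or noisy sensor does not turn into the mean breath curve. If transdermal readings alone give r > 0.9, the sensor has followed the rise and fall unaided, which is close to the aim in Section 4.1 of sensitivity to changes in BAL. This stands. A reader might infer that a non-working watch could be declared useful, and the documents do not support that.

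**The watch is not judged only against no relation.** Besides the 0.9 threshold there are the Cmax and Tmax correlations, the zero-BAL hour and the curve inspection. A mean-curve prediction gives every subject the same Cmax and Tmax, so those correlations would be undefined and would expose it. This also stands, but only in part. The Cmax and Tmax tests are themselves against zero, the inspection has no criterion, the zero-BAL hour does not vary the drinking pattern, and none of them feeds the usefulness rule.

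**Requiring the watch to beat the benchmark could reject a good device.** The benchmark is given the start time, the controlled intake and 12 subjects' breath curves, none of which is available in free-living use. At a peak CV of 18%, simulated genuine sensors with r of about 0.91 to 0.95 exceeded 0.9 and still lost to the time-only curve in 38% to 82% of trials. This stands and limits the remedy.

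**The size rests on unseen inputs.** That is correct: the chance that the time-only curve passes runs from about 100% to near zero over the assumed range. Dosing each subject by a body-water formula to one target peak is meant to narrow the spread, but the documents do not say by how much.

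**Conclusion.** The point holds in a limited form. Because both sessions repeat one drinking schedule, a prediction using only time since drinking began usually exceeds r = 0.9 when the CV of peak breath alcohol is up to about 25%. It seldom does so well above 30%, and around 30% the result depends on the kinetic assumptions (30% to 76% of trials). The 0.9 rule therefore shows tracking of breath alcohol under this schedule, but cannot by itself show information beyond the shared time course.

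This does not establish that the watch lacks information or that a failed sensor would pass. The other planned checks give partial protection outside the usefulness rule. The schedule and the criterion come from the documents; all kinetic, noise and variability values are assumptions. The plan should be changed on this point because the change needs only data already being collected and alters what the trial can conclude.

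**What to change.** **Section 12.1.** Pre-specify a time-only benchmark: the mean Phase I breath reading at each time since drinking began (first 4 hours), fixed before Phase II and applied unchanged to it. For the same subjects and time points, report:
- the repeated measures correlation and the root mean squared error (g/dL) against breath alcohol, for the benchmark and for watch-predicted BAL;
- the partial repeated measures correlation of predicted BAL with breath alcohol after adding the benchmark curve to the general linear model, with an interval that treats the subject as the unit.

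**Section 12.2.** State that r > 0.9 alone shows tracking of breath alcohol under this fixed schedule, and that a claim of information beyond the time course rests on the partial correlation. Do not make beating the benchmark's r a condition of usefulness: with 9 subjects and low between-subject spread that would often reject a working sensor.

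**Cost.** Some added wording, a little more analysis of data already collected, and a more cautious usefulness statement. No extra visits or subjects are needed.

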4.2 Study Outcome Measures

4.2.1 Primary Outcome Measures

The primary outcome is the correlation in estimated BAL as measured by the breathalyzer and the wristwatch sensor during the second alcohol self-administration trial. BAL and wristwatch sensor data correlation will be analyzed by repeated measures correlation (rmcorr) analysis, as described in more detail in section 12.

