Given that BAL and BrAc are expected to be equivalent it is also hypothesized that there will be a strong correlation between Cmax and Tmax values. Pearson correlation coefficients for correlation analysis between both Cmax and Tmax determined from individual subjects' BrAc and BAL curves, therefore, are expected to be 0.8 or greater, with p values being less than 0.05.

Hypothesis	Planned Analyses
1. There will be a significant correlation between BrAc predicted BAL measures	Repeated measures correlation analysis of wristwatch TAC measurements and contemporaneous BAC measurements from breathalyzer.
2. There will be a significant correlation between Cmax and Tmax values obtained for paired BrAc and predicted BAL measurements.	Pearson correlation analysis for Tmax and Cmax values obtained for BrAc and predicted BAL data.

We expect that the results of this study will demonstrate the effectiveness of the developmental wristwatch transdermal alcohol sensor. Furthermore, these results and the developmental work to calibrate this wristwatch will contribute significant knowledge toward the understanding of reliable measurement of blood alcohol via transdermal routes.

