If the existence of a time lag is found that precludes the usefulness of rcm values then Pearson correlations will be determined for AUC and Cmax values. For both of these value obtained for the TAC-BAL data for $r=0.8$, power will equal 0.82 for a sample size of 9 subjects who complete Phase I and Phase II. We anticipate consenting 36 subjects to achieve a sample size 12 randomizers and 9 completers.

Given that this is a laboratory-based experiment we do not plan to conduct any planned interim analyses in this study.

13 Ethics/Protection of Human Subjects

This study is to be conducted according to applicable US federal regulations and institutional policies (which are based in federal regulations, guidance, and ICH Good Clinical Practice guidelines).

This protocol and any amendments will be submitted to the Boston Medical Center and Boston University Medical Campus IRB, for formal approval of the study conduct. The decision of the

Calibration Study of a Wearable Noninvasive Blood Alcohol Monitor

Final V1.8 4.24.19

IRB concerning the conduct of the study will be made in writing to the investigator. A copy of the initial IRB approval letter will be provided to the sponsor before commencement of this study.

All subjects for this study will be provided a consent form describing this study and providing sufficient information for subjects to make an informed decision about their participation in this study. The consent form will be submitted with the protocol for review and approval by the IRB. The consent of a subject, using the IRB-approved consent form, must be obtained before that subject is submitted to any study procedure. Consent will be documented as required by the IRB.

14 References

1. Pantelopoulos, A. and N.G. Bourbakis, A survey on wearable sensor-based systems for health monitoring and prognosis. *IEEE Transactions on Systems, Man and Cybernetics, Part C (Applications and Reviews)*, 2010. 40(1): p. 1-12.
2. Allet, L., et al., Wearable Systems for Monitoring Mobility-Related Activities in Chronic Disease: A Systematic Review. *Sensors*, 2010. 10(10): p. 9026-9052.
3. Patel, S., et al., A review of wearable sensors and systems with application in rehabilitation. *Journal of Neuroengineering and Rehabilitation*, 2012. 9: p. 17.
4. Y. Hao, R. Foster, "Wireless Body Sensor Networks for Health Monitoring Applications," *Physiol. Meas.*, 29, R27-R56 (2008).

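### Sections 12.1 and 12.2 differ on which readings enter the primary correlation, so the r > 0.9 usefulness rule could be met from only the wearers on whom the watch detected alcohol

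*Combined protocol and SAP*

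**What the plan says.** Section 4.2.1 defines the endpoint: "The primary outcome is the correlation in estimated BAL as measured by the breathalyzer and the wristwatch sensor during the second alcohol self-administration trial". Section 12.1 describes the data set as the values at each time-point with a breathalyzer measurement and the corresponding predicted BAL. It does not mention zero or absent watch output.

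Section 12.2 counts up to 20 Phase II points per subject "if only pairs of data are used for which values for both devices exceed zero". It then warns that the "sensitivity of the wristwatch sensor in human subjects is currently unknown, and so fewer than 20 data points may be of use". The success rule is in the same section: "For the wristwatch device to be considered to be useful the r value for the correction between BrAc and predicted BAL measures must exceed 0.9". No minimum number of wearers, working watches or usable pairs goes with it. The section's power calculation uses SAS to "determine the power for 21 data points collected for 9 subjects and 10 datapoints for 5 subjects". The five are not explained.

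The secondary analyses use one value per subject: "Pearson correlation coefficients for correlation analysis between both Cmax and Tmax determined from individual subjects' BrAc and BAL curves". If a time lag makes the repeated measures correlation unusable, section 12.2 falls back on Pearson correlations for AUC and Cmax, for which "power will equal 0.82 for a sample size of 9 subjects who complete Phase I and Phase II" at r = 0.8.

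**The concern.** Section 4.1 asks whether the sensor is sensitive and reliable in people. A watch that runs through a dosed session and registers nothing is direct evidence against that. If only pairs with both devices above zero are used, such a wearer may contribute no pair, and a rule on r alone cannot register the loss. The same wearer has no defined Tmax, and the plan does not say whether Cmax and AUC are then zero or missing.

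The possibility is not remote on the plan's own account. Section 3.1 describes earlier work on skin-surrogate membranes, section 12.2 says sensitivity in humans is unknown, and section 9 gives Phase II subjects second-generation sensors. A choice between the two readings made after the data are seen could decide whether the device is called useful.

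**Working it through.** **The plan's own figures.** Section 12.2 takes Df = (subjects − 2) × (points − 1) and N = Df + 2.
- Nine subjects, 21 points: Df = 7 × 20 = 140, N = 142; power at r = 0.8 is about 1.000.
- Five subjects, 10 points: Df = 3 × 9 = 27, N = 29; power at r = 0.8 is 0.9999.
- Pearson fallback, n = 9, r = 0.8, two-sided 0.05: simulated power 0.820, against the stated 0.82.

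All reproduce. They are powers against zero correlation, not against the 0.9 rule, and they do not address which wearers are counted.

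**Effect of a flat watch on r.** Let Sxx, Syy and Sxy be the pooled within-subject sums of squares and products for breath alcohol (x) and predicted BAL (y). In the section 12.1 model, the breath-alcohol sum of squares is Sxy²/Sxx and the residual is Syy − Sxy²/Sxx. I take the formula's first term to be the breath-alcohol term. Then r = Sxy / sqrt(Sxx × Syy).

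A watch with constant output adds nothing to Sxy or Syy, whatever the constant, because the model fits a subject term. It does add to Sxx. With m working watches of nine and equal within-subject variation in breath alcohol, Sxx grows by 9/m, so

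r(all) = r(working) × sqrt(m/9).

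| Flat watches | m | sqrt(m/9) | r kept, if r(working) = 0.95 | r dropped |
|---|---|---|---|---|
| 0 | 9 | 1.000 | 0.950 | 0.95 |
| 1 | 8 | 0.943 | 0.896 | 0.95 |
| 2 | 7 | 0.882 | 0.838 | 0.95 |
| 3 | 6 | 0.816 | 0.776 | 0.95 |
| 4 | 5 | 0.745 | 0.708 | 0.95 |

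With two flat watches even r(working) = 1 gives only 0.882, below 0.9.

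**Simulation check.** These inputs are assumptions, because the documents give no sensor noise or non-detection rate:
- nine wearers with 16 readings, that is, one every 15 minutes over one hour of drinking and three of observation (section 12.2 counts 20);
- peak 0.05 g/dL, SD 0.0075, with a linear rise over one hour and then a fall of 0.015 g/dL per hour;
- watch noise SD 0.0045 g/dL truncated at zero, which gives r of about 0.95.

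The average breath curve ends at 0.05 − 3 × 0.015 = 0.005 g/dL, so a both-above-zero filter acts mainly on the watch.

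Share of simulated trials with r > 0.9:

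| Failed watches | Flat zero, filtered | Flat zero, all kept | Noisy, filtered | Noisy, all kept |
|---|---|---|---|---|
| 1 | about 100% | about 37% | about 91% | 32–39% |
| 2 | about 100% | 0% | about 29% | 0% |
| 3 | about 100% | 0% | 2–3% | 0% |
| 4 | about 100% | 0% | about 0% | 0% |

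A noisy failed watch carries positive noise of SD 0.001 or 0.0045 g/dL; the two give similar results. If whole curves are scaled between subjects instead, the flat-zero, all-kept figures are 46% for one failure and 0.7% for two.

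**The case against.** The strongest reply is that the plan does not order the exclusion. The both-above-zero wording is conditional and sits in a count of possible points. Section 12.1, which specifies the analysis, can be read as keeping zeros, so that a flat watch lowers r. This stands: the defect is that two passages point to different data sets, not that the plan states a rule to drop failures.

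A reader might also infer that the five-subject power case means the plan expects to score only five of its nine subjects. The documents do not support that. Section 12.2 gives no reason for the five, does not describe them as what remains of the nine, and words its worry as fewer data points.

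A third reply is that the near-certain pass after filtering needs a noiseless failed sensor. That is correct. With positive noise some pairs survive the filter and pull r down, as the last columns of the table show.

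Two safeguards might be cited. Section 12.1 plans to inspect sensitivity differences and individual curves, so a flat watch would be seen; but the inspection has no threshold and no link to the 0.9 rule. Section 9 replaces subjects unable to complete Phase II for any reason; it does not mention a wearer who attends, drinks and is observed with a non-detecting watch.

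Finally, keeping zeros mixes detection with linear agreement, and a count beside r might be thought enough. But a count alone would still let the 0.9 rule be met from responding watches only.

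**Conclusion.** The concern holds as an unresolved conflict between sections 12.1 and 12.2 that can change the conclusion. With flat-zero failures and r of about 0.95 in the working watches, dropping the failures leaves r near 0.95. Keeping them gives about 0.90 for one failure, which is borderline, and 0.84 or lower for two or more, which misses 0.9 if within-subject breath-alcohol variation is equal across wearers. With noisy failures the bias is smaller: for one failure about 91% against 32–39% of trials pass, for two about 29% against 0%, and beyond that there is little difference.

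The sizes rest on the assumed curve, noise and r(working). The direction rests only on the missing rule and on a criterion that ignores how many watches responded. If every watch detects alcohol in Phase II, the issue has no effect at wearer level.

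**What to change.** In sections 12.1 and 12.2:
- Remove the both-above-zero condition for the primary r. Use the section 12.1 set: all breathalyzer time-points from every subject dosed in Phase II who wore a running watch.
- Enter non-detection as the model's predicted BAL at zero transdermal alcohol. Do the same for Cmax and AUC, and count Tmax for a flat watch as not detected.
- Apply the r > 0.9 rule to that set. Report beside it the number of dosed wearers with a detectable response (k of n, exact 95% confidence interval).
- Exclude only documented hardware failures with no data logged, and report their count.

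The cost is wording and one count with an interval, with no new subjects or measurements. The downside is a less favourable r if any watch fails to detect alcohol.
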